# Continuing Review

## Basic Info

Confirmation Number: **chbgaide**  
Protocol Number: **828183**  
Created By: **[name]**  
Principal Investigator: **[name]**  
Protocol Title: **Use of A Telehealth Intervention to Decrease Readmissions in Cirrhosis: A Randomized Controlled Trial**  
Short Title: **Telehealth RCT in Cirrhotics**  
Protocol Description: **The proposed study is a randomized controlled trial comparing a simple telehealth intervention implemented after hospital discharge to standard of care for reducing hospital readmissions. All cirrhotic patients admitted to the Hepatology service at The Hospital of the University of Pennsylvania will be randomized to one of the two arms outlined above. Patients will be followed for 90 days. Rates of 30 and 90 day readmission will be compared between the groups.**  
Submission Type: **Social and Biological Sciences**  
Application Type: **FULL**

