#### **Design**

A randomized controlled trial will be conducted. The 2 potential groups to which patients may be randomized are: 1) a simple telehealth intervention that utilizes the Way to Health Platform to send SMS messages directly, and 2) standard of care. Given that assignment to the interventions will be obvious to the participants, study staff and investigators, no blinding procedures will be employed. Of note, any participant randomized to the usual care arm will be offered 90 days of telehealth monitoring after study completion.

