#### **Study duration**

The estimated length of the study will be approximately one year. Each participant will be enrolled for a period of 90 days. The period of follow up will begin on the discharge day and end exactly 90 days from that date. Once patients have completed the 90 days of observation, they are not permitted to be re-enrolled in the study. If a control patient chooses to receive telehealth text messages after the 90 days, they will be in the study for up to 180 days.

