### Procedures

All cirrhotics admitted to the Hospital of the University of Pennsylvania between the ages of 18 and 80 will be approached for consent (see attached consent forms in the designated section of the protocol). If patients are missed due to being discharged on the weekend, during a holiday or timing issue, patients may be contacted by phone to enroll in the study. If interested, patients can give verbal consent over the phone or written consent at their following clinic visit. After consent is obtained and information is entered into the Way to Health Platform, the participant will be randomized. During this period of time, the participant will be asked to complete the quality of life assessments/ program surveys. Depending on the group to which they are randomized, those in the intervention group will receive welcome items (scale, stop watch, and binder, all necessary for proper data collection in the intervention group). Those randomized to the usual care arm will receive their standard discharge paperwork. Clinical data (readmissions, reasons for readmissions, and length of stay) will be determined for both groups at 30 and 90 days. The groups will additionally be asked to complete quality of life assessments at the end of the study period and a program assessment in the middle and end of the protocol. Additionally, as assessment of readmission rates will be determined in both groups for another 90 days after the end of the intervention (to determine if the health behaviors learned in the intervention group are durable and to determine if providing the intervention to those in the usual care arm is beneficial even if there is a delay in initiation).

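### Days 91–180: the follow-up sections conflict, and randomisation alone cannot separate durability from delayed benefit

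*Protocol*

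**What the plan says.** Three sections of the protocol set the length of follow-up.

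- Basic Info (protocol description): "Patients will be followed for 90 days".
- Study duration: "The period of follow up will begin on the discharge day and end exactly 90 days from that date". The one exception is a control patient who "chooses to receive telehealth text messages after the 90 days, they will be in the study for up to 180 days".
- Procedures: "readmission rates will be determined in both groups for another 90 days after the end of the intervention".

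Procedures attaches two purposes to the extra window. For the telehealth arm it is "to determine if the health behaviors learned in the intervention group are durable". For the usual care arm it is "to determine if providing the intervention to those in the usual care arm is beneficial even if there is a delay in initiation".

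The Design section says that "any participant randomized to the usual care arm will be offered 90 days of telehealth monitoring after study completion". Group Modifications, Study duration and Potential Study Benefits describe the same offer, and acceptance is the patient's choice. The later window does not appear in the overall objectives or in the primary and secondary outcome variables, and the Analysis Plan does not mention it.

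**The concern.** There are two separate problems.

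The first is a conflict over who is followed. If staff work from Study duration, readmissions after day 90 are gathered only for usual care patients who take up telehealth. The assessment in Procedures needs both whole arms, and no later analysis document can restore data that were never collected.

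The second is what the data could show if they were collected. Once the whole usual care arm has been offered telehealth, no randomised group is held off it during days 91–180. Both purposes are worded as questions the window will settle. A small difference between the arms could be misread as showing that the effect does not last, or that late telehealth does not help, when it shows neither.

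**Working it through.** **Step 1. The sections side by side, by patient group, for days 91–180**

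| Group | Study duration | Procedures |
|---|---|---|
| Telehealth arm | follow-up over at day 90 | readmissions determined |
| Usual care, accepts telehealth | in the study up to day 180 | readmissions determined |
| Usual care, declines | follow-up over at day 90 | readmissions determined |

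The sections agree only on the middle row. The description in Basic Info makes no exception for any row.

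**Step 2. What the randomised contrast contains**

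The protocol gives no figures for this window, so there is none to reproduce and every input below is an assumption. Let q be the untreated readmission risk in days 91–180, e the initial relative effect of telehealth (above zero), p the share of it that persists, u the uptake in usual care, and d the relative effect of delayed telehealth in those who take it. Takers and decliners are assumed to have the same untreated risk.

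- Former telehealth arm: q(1 − p·e)
- Usual care arm: q(1 − u·d)
- Difference, former telehealth minus usual care: D = q(u·d − p·e)

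Uptake u is observed, and e can be estimated from days 0–90. That leaves one equation with p and d both unknown. Solving for p gives p = u·d/e − D/(q·e).

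**Step 3. A difference of zero**

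With D = 0, p = u·d/e. Let d run from 0 (late telehealth does nothing) to e (it works as well as the first course). Then p runs from 0 to u, whatever q and e are:

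| Assumed uptake | Persistence compatible with D = 0 |
|---|---|
| 25% | 0–25% |
| 50% | 0–50% |
| 75% | 0–75% |

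Take q = 0.40, e = 0.30 and u = 0.50 as an example.

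- Neither effect present (p = 0, d = 0): both arms are at 0.40.
- Half the effect persists and late telehealth works fully (p = 0.50, d = 0.30): telehealth arm 0.40 × (1 − 0.15) = 0.34; usual care 0.40 × (1 − 0.50 × 0.30) = 0.34.

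D is zero in both cases.

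**Step 4. A difference away from zero**

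Use the same q, e and u, so that q·e = 0.12.

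- D = +0.03 (former telehealth arm worse): p = 0.50·d/e − 0.25. Since p cannot be negative, d/e lies between 50% and 100% and p between 0 and 25%. Some delayed benefit is implied.
- D = −0.03 (former telehealth arm better): p = 0.50·d/e + 0.25, so p lies between 25% and 75%. Some persistence is implied, while d/e may still be anything from 0 to 100%.

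The sign of the difference therefore carries information. The first reading needs earlier telehealth to leave no later harm; the second needs delayed telehealth to do none.

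**Step 5. Readings within one arm**

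Comparing days 0–90 with days 91–180 inside an arm is not a randomised comparison. The Background reports that about half of potentially preventable readmissions occur within 10 days of discharge, so a later window may look better with no treatment effect at all. In usual care, the comparison also depends on who chose telehealth.

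**The case against.** The strongest reply is that this is a supplementary window. Procedures attaches one question to each arm and commits to no between-arm test, and the method could properly be left to an analysis plan that is not shown. The follow-up conflict also has a workable reading. The protocol often uses study or observation period for the first 90 days, and Procedures presents the second 90 days as an addition. Offering telehealth to the control arm is a deliberate choice.

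Much of this stands. It is fair to call the conflict a matter of clarification, and the persistence ranges illustrate non-identification rather than measure harm to this trial. In particular, saying that D = 0 allows a delayed effect from none to full only means that the data do not narrow the assumed range.

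It does not remove the point. Study duration speaks of the follow-up period itself and names a single exception, which does not cover two of the three groups. The two purposes are the protocol's own statements, and leaving the method open does not supply an untreated randomised group.

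A reader might infer more than the document supports:

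- *That the late offer contaminates the main result.* It does not. Group Modifications withholds messages from usual care until its observation period is complete.
- *That days 91–180 can teach nothing.* Step 4 shows otherwise; the full ambiguity applies near zero.
- *That the later data cannot exist.* That follows only from the strictest reading of Study duration.
- *That the stated duration is wrong.* The protocol says "The estimated length of the study will be approximately one year" but gives no enrolment rate for the trial, so follow-up to day 180 is a reason to check that figure, not proof of an error.

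**Conclusion.** The point holds in two parts. Basic Info and Study duration contradict Procedures on follow-up after day 90 for telehealth-arm patients and for usual care patients who decline the offer. In addition, randomisation alone cannot answer the durability and delayed-benefit questions separately. With a zero difference, persistence could be anything from none up to the uptake share. That result assumes equal untreated risk in takers and decliners and a delayed effect between none and the full initial effect; it does not depend on the untreated risk or the size of the initial effect.

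The weight is low to moderate. The window lies outside the stated objectives and outcomes, and the primary 30- and 90-day comparison is untouched.

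**What to change.** 1. Reconcile Basic Info, Study duration and Procedures so that readmissions are collected to day 180 for every randomised participant in both arms, whether or not telehealth is accepted, by the same means as for days 0–90.
2. Replace the two purposes in Procedures with an exploratory, descriptive report of readmissions in days 91–180 by randomised arm, together with telehealth uptake in usual care.
3. Label any between-arm contrast in or through that window as immediate versus delayed offer of telehealth, not as durability or delayed benefit.

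The cost is mainly wording, since Procedures already intends the extra collection and the offer to usual care stays as it is. Two exploratory causal claims are given up, and the one-year estimate should be checked against follow-up to day 180.

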**The following documents are currently attached to this item:**

*There are no documents attached for this item.*

**Deception**

Does your project use deception?

No

**Analysis Plan**

The primary analysis will include a comparison of the demographics and clinical data for the intervention group and the usual care group. To determine if there is a difference in the rates of readmission between the groups, univariable logistic regression analysis will be performed. Any predictors which were different between the groups will be used for adjustment in a multivariable logistic regression. We plan to analyze the data at the 6 month mark. If a significant difference is found, given the low cost of the intervention and potential benefits, the study will be stopped and all patients admitted to the hepatology service will be eligible for telehealth monitoring. Data for the secondary outcomes including changes in quality of life and patient satisfaction will be explored.

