#### **Method for Assigning Subjects to Groups**

Describe how subjects will be randomized to groups.

Permuted block randomization will be utilized to randomize patients to the intervention and usual care arms, maintaining a 1:1 ratio as determined most efficient for obtaining the necessary sample size but decreasing the ability of study staff to know to which group a new participant will be assigned. All randomization procedures will be executed on the Way to Health Platform.

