### **Background**

It is well known that patients with cirrhosis have high morbidity and mortality and that early re-hospitalization in any disease process is known to be costly and partially preventable. Few studies exist in the literature on the topic of readmissions in cirrhosis and none use a patient centered approach or a telehealth strategy to reduce readmissions and improve quality of care nor impact quality of life. Volk et al. demonstrated in 2012 that rates of hospital readmission among patients with cirrhosis are higher than other diseases such as CHF, making this patient group at high risk for poor health outcomes. Predictors of readmission include Model For End Stage Liver Disease, MELD, score, serum sodium, and number of concomitant medications used. Frequent readmissions are independently associated with increased mortality, making this not just an economic but also a human concern. The 1st and 2nd most common causes for readmission in cirrhotics are fluid imbalances (overload or dehydration) and hepatic encephalopathy (HE) or confusion resulting from liver disease. Overt HE occurs in 30-40% and minimal HE in 20-80% of patients with cirrhosis. It presents a unique clinical challenge not present in most populations with severe underlying medical conditions as confusion can lead to poor adherence with treatment, making cirrhotics arguably one of the highest risk populations for poor health outcomes. Unfortunately, little attention has been paid to this area thus far. More recently the NACSELD consortium, a 14 center group of liver transplant centers including Penn, showed a 53% 90-day readmission rate for cirrhotics (Bajaj et al). Discrete data from the consortium is limited compared to that from single center studies and no intervention was performed to decrease readmissions or improve patient involvement in their care through this consortium. Authors Tapper, Kumral and Fortune have shown in the last year that readmission rates of cirrhotics at their liver transplant centers are 38%, 62%, and 40%. At The Hospital of the University of Pennsylvania, the 30-day readmission rate for cirrhotic patients is 28%. The hepatology service at the Hospital of The University of Pennsylvania has the highest percentage of potentially preventable readmissions (PPRs) of any service (23.3%) and

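### The adjusted readmission model takes its covariates from chance imbalance between randomised arms instead of the predictors the protocol already names

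*Protocol*

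**What the plan says.** The Analysis Plan of the protocol sets out three steps.

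- A comparison of the arms: "The primary analysis will include a comparison of the demographics and clinical data for the intervention group and the usual care group".
- An unadjusted model: "To determine if there is a difference in the rates of readmission between the groups, univariable logistic regression analysis will be performed".
- An adjusted model whose content depends on the first step: "Any predictors which were different between the groups will be used for adjustment in a multivariable logistic regression".

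It gives no criterion for different, lists no covariates, and does not say outright which of the two models decides. The univariable model reads as the deciding test. The same section adds an earlier look: "We plan to analyze the data at the 6 month mark".

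Two other sections bear on this. Under Method for Assigning Subjects to Groups: "Permuted block randomization will be utilized to randomize patients to the intervention and usual care arms, maintaining a 1:1 ratio". No stratification factor is stated there. Under Background: "Predictors of readmission include Model For End Stage Liver Disease, MELD, score, serum sodium, and number of concomitant medications used". Nothing elsewhere in the protocol fixes covariates or overrides the rule.

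**The concern.** A covariate is worth including because it predicts the outcome. Under randomisation, an observed difference between arms in a pre-randomisation variable is chance and carries no information about prognosis. A rule that admits covariates only when they differ will therefore usually leave out the variables that would sharpen the comparison, even though the protocol has already identified three.

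The rule also makes the model unpredictable. Applied at 6 months and again at the end, it can produce two different adjusted models in the same trial. If one of them disagrees with the univariable result, the protocol offers no way to settle which counts.

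At stake are a modest amount of power and the interpretability of the adjusted result. Type I error is not the issue. How alpha is handled at the 6-month look is a separate question and is not raised here.

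**Working it through.** **Inputs from the protocol.** About 426 participants (Abstract), so 213 per arm at 1:1. A 28% 30-day readmission rate at the site and a 53% 90-day rate from a consortium (Background). Three named predictors (Background). Length about one year (Study duration). The protocol gives no alpha, power or effect size with the 426, so there is no power figure to reproduce.

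**Assumptions, not in the protocol.** Different means p<0.05, with p<0.10 and p<0.20 as alternatives. The candidates are only the three named predictors. Their log odds ratios per SD are weak (0.26 each), moderate (0.5, 0.3, 0.3) or strong (0.7, 0.4, 0.4). The effect gives about 79% unadjusted power: 28% v 16.8%, or 53% v 39.6%.

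**Step 1. How often the rule picks up the known predictors.** For three independent predictors and cut-off α, P(none selected) = (1−α)³ and P(all selected) = α³.

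| Cut-off | None of the three | All three |
|---|---|---|
| 0.05 | 0.95³ = 0.857 | 0.000125 |
| 0.10 | 0.90³ = 0.729 | 0.001 |
| 0.20 | 0.80³ = 0.512 | 0.008 |

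**Step 2. Power.** Simulation with 213 per arm, normally distributed predictors, Wald tests at 0.05 and 10,000 trials per setting. The Monte Carlo standard error of each paired gain over the rule is 0.2 to 0.3 points.

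| Control rate, correlation | Strength | Unadjusted | Rule | Prespecified |
|---|---|---|---|---|
| 28%, 0 | weak | 0.790 | 0.792 | 0.803 |
| 28%, 0 | moderate | 0.795 | 0.795 | 0.818 |
| 28%, 0 | strong | 0.798 | 0.803 | 0.841 |
| 53%, 0 | weak | 0.786 | 0.787 | 0.810 |
| 53%, 0 | moderate | 0.788 | 0.790 | 0.828 |
| 53%, 0 | strong | 0.783 | 0.789 | 0.851 |
| 28%, 0.3 | weak | 0.800 | 0.803 | 0.820 |
| 28%, 0.3 | moderate | 0.795 | 0.799 | 0.836 |
| 28%, 0.3 | strong | 0.792 | 0.801 | 0.862 |
| 53%, 0.3 | weak | 0.794 | 0.797 | 0.826 |
| 53%, 0.3 | moderate | 0.787 | 0.796 | 0.845 |
| 53%, 0.3 | strong | 0.783 | 0.796 | 0.869 |

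From unrounded results, prespecified adjustment gains the following, in points of power:

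- over the rule: 1.1 to 6.1 (independent) and 1.7 to 7.3 (correlation 0.3);
- over no adjustment: 1.2 to 6.8 and 2.0 to 8.6.

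The rule gains 0.0 to 1.3 over no adjustment. With looser cut-offs and independent predictors (6,000 trials per setting), the gain over the rule is 1.0 to 5.9 at p<0.10 and 0.9 to 4.7 at p<0.20.

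A separate simulation with ten candidate covariates, three of them prognostic (log odds ratios 0.6, 0.5, 0.4), and a smaller effect gave power of 62% unadjusted, 62% under the rule and 68% prespecified.

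**Step 3. Type I error.** Under no effect (8,000 trials per setting, independent predictors): unadjusted 4.3 to 4.9%, rule 4.2 to 4.8%, prespecified 4.7 to 5.0%. Rejecting if either the unadjusted or the rule-based model is significant: 4.6 to 5.1%.

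**Step 4. Stability between the two analyses.** Let t be the share of the final sample analysed at 6 months. The two balance statistics for one predictor are bivariate normal with correlation √t. With P₁₁ the chance of selection at both analyses, its status changes with probability q = 0.05 + 0.05 − 2P₁₁, and the set of three changes with probability 1 − (1 − q)³. Even accrual over 9 months of a one-year study (assumed) gives t = 3/9 with 90-day follow-up complete and t = 5/9 with 30-day follow-up complete.

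| t | P₁₁ | q | Set changes | Set changes, given something selected at 6 months |
|---|---|---|---|---|
| 1/3 | 0.0117 | 0.0767 | 0.213 | 0.794 |
| 1/2 | 0.0169 | 0.0662 | 0.186 | 0.696 |
| 5/9 | 0.0188 | 0.0624 | 0.176 | 0.659 |

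The last column applies to the 1 − 0.857 = 14.3% of trials that select something at 6 months, which is about 9 to 11% of all trials.

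**The case against.** The strongest reply is about attribution. If the univariable regression decides, the imbalance rule costs that decision nothing, and an unadjusted primary analysis is a legitimate choice. The power gain then comes from moving to an adjusted primary analysis and not from removing the quoted sentence. This is right as far as it goes. The defect in the sentence itself is an adjusted result with chance-chosen content, and deleting it would be the minimal repair.

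The size also rests on assumed predictor strengths and an assumed cut-off. That stands: the weakest setting gives about 1 point, the 86% falls to 51% at p<0.20, and an informal judgement of imbalance was not modelled. The direction is the same in every setting.

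The word predictors might mean only known readmission predictors. The simulation already takes that reading, which favours the rule, and entry still depends on chance imbalance.

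Finally, the protocol does not say that the compared clinical data are baseline values, and its Procedures section uses that term for readmissions, their reasons and length of stay. The chance argument holds only for pre-randomisation variables. Adjusting for anything measured afterwards would be worse, so this ambiguity is a further reason to name the covariates and their timing.

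**Conclusion.** The concern holds. The protocol states a covariate rule that randomisation makes uninformative, and passes over three predictors that it names itself. The consequences are modest: on the stated assumptions, a power loss of about 1 to 7 points against prespecified adjustment, and an adjusted model whose content may change between the 6-month and final analyses. The unadjusted test remains valid and type I error stays near 5%. The change should be made because it is cheap, not because the trial would otherwise mislead.

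**What to change.** Replace the sentences "To determine if there is a difference in the rates of readmission between the groups, univariable logistic regression analysis will be performed" and "Any predictors which were different between the groups will be used for adjustment in a multivariable logistic regression" with:

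> At each readmission time point analysed, the arms are compared by logistic regression of readmission on randomised arm, adjusted for MELD score, serum sodium and number of concomitant medications (last value before randomisation), whatever the observed balance. A missing baseline value is replaced by the mean over both arms. This model supplies the test at the 6-month and the final analysis. The unadjusted logistic regression is a sensitivity analysis, and the arm percentages are reported beside the odds ratio. Baseline comparisons are descriptive and do not select covariates.

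If the three values cannot be obtained, keep the univariable model as the deciding test and delete the imbalance rule. That needs no new data.

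The cost is two sentences and, if they are not already collected, three routine chart values per participant. Some values may be hard to get, since patients can qualify through an outside hospital admission or enrol by phone after discharge. With 15% of each value missing (assumed) and mean imputation, the gain over the rule is still 0.8 to 5.0 points with independent predictors and 1.5 to 6.6 with correlation 0.3. The odds ratio becomes conditional on the covariates, which is why the arm percentages must stand beside it. The wording does not settle how alpha is shared between the two analyses; that has to be dealt with separately.

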## Protocol

### **Abstract**

To compare rates of 30 and 90-day readmission of cirrhotic patients to The Hospital of the University of Pennsylvania randomized to telehealth monitoring, as administered by the Way to Health Platform, or usual care. 2. To use a patient centered approach to determine the specific interventions which are most helpful as perceived by patients and have an impact on quality of life. Approximately 426 subjects will be enrolled.

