### **Objectives**

#### **Overall objectives**

1. To compare rates of 30 and 90 day readmission of cirrhotic patients to The Hospital of the University of Pennsylvania randomized to telehealth monitoring, as administered by the Way to Health Platform, or usual care. 2. To use a patient centered approach to determine the specific interventions which are most helpful as perceived by patients and have an impact on quality of life.

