#### **Primary outcome variable(s)**

A decrease in readmission rates of cirrhotic patients.

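### The month-6 stopping rule is triggered by an unqualified significant result, with no boundary and no named readmission window; at p<0.05 for both looks the type I error on one endpoint is about 8–9%

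*Protocol*

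**What the plan says.** The Analysis Plan sets the timing, "We plan to analyze the data at the 6 month mark", and the consequence, "If a significant difference is found, given the low cost of the intervention and potential benefits, the study will be stopped". Once stopped, all hepatology admissions become eligible for telehealth. The same paragraph describes a univariable logistic regression and then an adjusted one, without saying which decides the stop.

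The outcome that the rule reads is not fixed. Primary outcome variable(s) gives only "A decrease in readmission rates of cirrhotic patients". The Basic Info description ("Rates of 30 and 90 day readmission will be compared between the groups"), the Abstract ("To compare rates of 30 and 90-day readmission of cirrhotic patients") and the Overall objectives ("To compare rates of 30 and 90 day readmission of cirrhotic patients") name both windows without ranking them. Under Procedures, readmission data "will be determined for both groups at 30 and 90 days".

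Study duration gives about one year in total and 90 days of follow-up per participant from discharge. The Abstract gives about 426 participants. Data and Safety Monitoring leaves review of the data to the PI and co-investigator, with no DSMB, and the Design section says there is no blinding.

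**The concern.** This is a complete decision rule: a date, a trigger and an action. The trigger is met by any result that would ordinarily be called significant, on either time point. Testing accumulating data twice at the usual level raises the chance of a false claim, and leaving two unranked endpoints open raises it further.

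A false benefit at month 6 would end the trial and change care across the service, after which a randomised usual-care comparison there would be hard to resume. A real but modest benefit would tend to be overstated, because only large observed differences reach p<0.05 in a small interim sample. With no independent committee and no blinding, the prespecified rule is the main safeguard.

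**Working it through.** The protocol states no alpha, power, target effect or boundary, so there is no error rate of its own to reproduce. The figure of 426 fits many combinations of inputs and can be neither confirmed nor refuted; the point does not depend on it.

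**Information at month 6.** Assume uniform accrual over A months, with A = 12 (accrual fills the year) or A = 9 (the last 90 days of follow-up fall inside the year). Fraction complete: t = (6 − 3)/A for 90-day outcomes and (6 − 1)/A for 30-day outcomes.
- 90-day: 3/12 = 25% (about 107 of 426) to 3/9 = 33% (142 of 426).
- 30-day: 5/12 = 42% (about 178) to 5/9 = 56% (about 237).

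**One named endpoint.** Assume two-sided 0.05 at both looks. Overall error = 1 − P(|Z1| < 1.96 and |Z2| < 1.96), with Z1, Z2 bivariate normal and correlation √t.

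| t | Either direction | False benefit only (nominal 2.5%) |
|---|---|---|
| 25% | 9.07% | 4.54% |
| 33% | 8.83% | 4.42% |
| 42% | 8.58% | 4.29% |
| 50% | 8.31% | 4.16% |
| 56% | 8.12% | 4.06% |

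**Either time point may count.** Null trials were simulated with 213 per arm, nested 30- and 90-day events and 400,000 replicates per setting. The 30-day rate is 28% (the hospital's own figure in Background). The 90-day rate is 53%, from the multicentre source that "showed a 53% 90-day readmission rate for cirrhotics", varied from 38% to 62%. Those outer values are other centres' rates, given without a time point, so they serve only as a range.
- Success on either endpoint at either look: 13.7–16.3%; false benefit 6.8–8.2%.
- Either endpoint at the final look only: 7.9–9.2%. That part comes from the two endpoints; the interim look adds about 6–7 points.

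**Overstatement when the trial stops for benefit.** 90-day outcome, 53% control rate, stop at p<0.05 in favour of telehealth, 400,000 simulated interim analyses. Arm sizes are 142/2 = 71 and about 107/2 = 53.

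| True reduction (points) | Mean estimate, 71 per arm | Mean estimate, 53 per arm | P(stop at p<0.05), 71 per arm | P(stop at p<0.001), 71 per arm |
|---|---|---|---|---|
| 10 | 21.0 | 24.5 | 22.9% | 1.7% |
| 15 | 22.4 | 25.5 | 44.5% | 6.5% |
| 20 | 24.3 | 26.8 | 68.2% | 18.5% |

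The exaggeration is about twofold for a true 10 points and shrinks as the true effect grows.

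**Boundaries that control the error.**
- Haybittle-Peto (p<0.001, then 0.05): overall 5.06%, 5.05% and 5.02% at t = 25%, 33% and 50%.
- O'Brien-Fleming-type spending: p<0.0002 then 0.0499 at t = 33%; p<0.003 then 0.049 at t = 50%.
- Pocock-type: p<0.0277 at both looks at t = 33%; p<0.0294 at both at t = 50%.

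**The case against.** The strongest reply is that a protocol may leave the boundary to the SAP, and that a significant difference can be read as one that crosses an adjusted boundary. The protocol states 0.05 at neither look, so the 8–9% rests on two unstated choices. That is true, and the figure is conditional. But the protocol does more than stay silent: it states the trigger, and ordinary significance satisfies it. With a stricter SAP boundary, a month-6 result of p = 0.03 would stop the trial under one document and not under the other, so the protocol sentence needs changing either way.

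Second, roll-out follows only from the month-6 look, where a false benefit on one named endpoint at two-sided 0.05 has a probability of about 2.5%. This is correct. The 8–9% is the error of the trial's overall claim in both directions; the like-for-like benefit figure is 4.1–4.5% against 2.5%.

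Third, the unranked time points are partly a separate problem. That is fair, and the 14–16% is split accordingly above. The one-endpoint result stands without it.

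Fourth, Background reports 54–65 cirrhotic admissions a month, so 426 could in principle be reached in 426/65 = 6.6 to 426/54 = 7.9 months. That would need every admission to be a new, consenting patient. At A = 7, information would be 3/7 = 43% (90-day) and 5/7 = 71% (30-day), with errors of about 8.5% and 7.5%. The conclusion is unchanged.

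Finally, the rationale given in the rule makes sense only for benefit. That is a natural reading, but the text does not say so.

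**Conclusion.** The concern holds. As written, the rule lets a conventional significant result on an unspecified readmission window end the trial and start roll-out. With two-sided 0.05 at month 6 and at the end, and uniform accrual over 9–12 months, the type I error is 8.1–9.1% for one endpoint (false benefit 4.1–4.5% against 2.5%). It is about 14–16% if either window may count, of which about 8–9% would exist without the interim look. Under the same accrual assumption, only 25–33% of 90-day outcomes would be complete at month 6, and stopping for benefit then would on average report a true 10-point reduction as 21–25 points. The level and the accrual pattern are assumptions, but inflation persists across the accrual patterns examined. The rule should be corrected before the month-6 analysis.

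**What to change.** Amend the Analysis Plan and Primary outcome variable(s):
- Name one primary time point, 30 or 90 days at the investigators' choice, and make the other secondary.
- Name the model, unadjusted or adjusted, that decides the stop.
- Base the month-6 look only on participants whose window for the primary outcome has closed.
- Replace the unqualified trigger with a stated boundary, for example Haybittle-Peto two-sided p<0.001 with the final test at 0.05. O'Brien-Fleming-type spending is an alternative where strict 5% control is wanted. A Pocock-type boundary also controls the error and keeps early stopping more likely, at the price of a stricter final test.
- State that only a difference favouring telehealth triggers the stop and the extension to all admissions.

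This costs a few sentences and no extra patients. One time point loses primary status, and early stopping becomes rarer: with 71 per arm and a 53% control rate, the chance of stopping at p<0.001 is about 2%, 7% and 18% for true reductions of 10, 15 and 20 points, against 23%, 45% and 68% at p<0.05.
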